8.3. Sample Acquisition

Patient Protections

- Each patient sample set will be coded with a unique patient identifier. No patient specific information is encoded in this ID. The protocol scientific investigator(s) handling the samples will be blinded as to the patient identification, patient data and outcome.
- Blood samples obtained by and stored through the Clinical Pharmacology Core will be labeled with unique barcodes.

Tumor Samples

- **Biopsies:** At least two core biopsies representing 18-gauge x at least 1cm in length, will be obtained. Inability to get tissue with a reasonable attempt will not preclude treatment and the patient will remain eligible for all other translational endpoints. Should CT scans be needed for safe core biopsy, a limit of 10 slices for each procedure will be observed to minimize radiation exposure to the patient.
- **Skin:** Where subcutaneous or skin is involved, two 2-3mm full thickness punch biopsies may be obtained.
- **Malignant effusions:** Known malignant effusions (pleural or peritoneal) may be acquired as the tissue sample in lieu of core tissue biopsies. Where both are present, the decision as to which sample to obtain will be made jointly between the patient, interventional radiology, and the research team.

Tumor Sample Handling

- **Core needles biopsy** samples are to be immediately embedded and frozen in OCT on dry ice on site and stored in liquid nitrogen until use. Biopsy scheduling and acquisition of research samples will follow the standard procedures for Special Procedures/Interventional Radiology and research sampling subjects protection. Members of the [name] lab will be on call to receive, label, embed, and store biopsies Phone: beeper [name].
- **Skin biopsies** will be embedded in OCT on site upon receipt, frozen in dry ice, and stored in liquid nitrogen until use. Members of the [name] lab will be on call to receive, label, embed, and store biopsies Phone: beeper [name].
- **Malignant Effusions:** A minimum of 50ml of non-heparanized effusion will be picked up by the [name] laboratory. Ten aliquots of supernatant and 10 viably frozen cell pellets will be stored in liquid nitrogen until use.

Blood Sample Requirements

- **Circulating Endothelial Cells (CEC):** Three 8 cc CPT-citrate tubes (Tiger top: blue and black top) will be drawn pretreatment and the day of repeat imaging and biopsy. The [name] laboratory ([name], [contact]) will be contacted to confirm scheduling and will be called [contact] when the sample is ready. The sample is to be kept at room temperature until pick up.
- **Circulating Cytokines:** An approx 8-10ml clot tube and an 7 ml green top (heparin) tube (or volume equivalents) will be obtained prior to treatment and the day of repeat imaging and biopsy. The tubes will be packed on wet ice and picked up by the Clinical Pharmacology Core ([name] (Call [contact] – [name] with any questions). Serum and plasma will be separated and aliquoted according to the CPC SOPs and stored, barcoded, in the CPC repository until use.
- **PBMC PAR Incorporation:** Three 8 ml CPT-citrate tubes (Tiger top) will be obtained prior to treatment and the day of repeat imaging and biopsy. PBMCs will be isolated according to CPC SOP, aliquoted and stored, barcoded, in the CPC repository until use ([name] (Call [contact] – [name] with any questions).
- **Pharmacogenomics:** A single purple top tube (EDTA – minimum of 7 cc) will be collected prior to initiation of therapy. Sample will be placed on wet ice and refrigerated. The CPC will be paged for pickup at [name] (Call [contact] – [name] with any questions). DNA extraction and analysis will follow the CPC pharmacogenomics SOPs.

8.4. **Functional Imaging**

- Patients will be scheduled with the Molecular Imaging Program of the Center for Cancer Research, NCI. No special preparation is required with the exception of recent electrolyte results and placement of a venous access device.
- Index lesions will be selected for serial measurement based on size (preferably at least 2 cm in largest diameter) and relative immobility. Scans will be obtained on the same schedule as the tumor biopsies.

- Conventional T1 and T2 weighted images of the target lesion will be obtained and a T1 map will be generated. This will be followed by a series of 3D gradient echo T1 weighted dynamic sequence which will be acquired before, during and after the administration of 0.1mmol/kg of a gadolinium chelate. Approximately 6 images are obtained prior to the administration of contrast media and the data collection continues of 5 minutes after injection. Data is transferred to an independent workstation and will be analyzed using a modified general kinetic model. This model generates two parameters K_{trans} and k_{ep} (permeability terms) which will be used as continuous outcome variables in the analysis. Vascular fraction may also be assessed. Color maps based on these parameters will also be generated. Data obtained before and on therapy will be compared for changes as a result of decreases in angiogenesis.

8.5. **PAR Incorporation**

A validated commercial PAR ELISA (Trevigen) will be used to quantitate PAR labeling in batched PBMC aliquots.

8.6. **Circulating Endothelial Cells (CEC)**

CEC and circulating endothelial precursors (CEP) will be analyzed by multi-parameter flow cytometry. Cells will be analyzed for forward and side scatter, and a dump channel will be created to exclude cells expressing hematopoietic markers, such as CD45. Endothelial cells will be identified using co-expression of markers, such as CD31 and CD146 for mature endothelial cells, and CD133 for CEP cells. The cell populations will also be analyzed for viability using scatter profiles and a vital stain, such as Hoechst 33258. Percentages of stained cells will be determined and compared with appropriate negative controls. Multi-parameter flow analysis will be performed with a BD LSR II equipped with FlowJo software, using a minimum of 500,000 events per analysis in the [name] Laboratory.

8.7. **Circulating Cytokines**

VEGF, IL6, and IL8, among other pro-angiogenic cytokines have been shown to be induced during anti-angiogenic therapy as a pharmacodynamic measure of angiogenesis inhibition, including in cediranib in several cancers. Plasma will be collected and rapidly separated and stored. Samples will be batched and cytokines measured in at least duplicate using commercially available ELISA kits (most are available from R&D). A minimum of the following cytokines will be examined: VEGF, IL6, IL8. Others that may be considered include but are not limited to: sVEGFR2, Ang2, PIGF.

8.8. **Pharmacogenomics, PARP and XRCC1 Polymorphisms**

Multiple polymorphisms of the PARP-1 protein have been described (Cottet et al., 2000; Hur et al., 2006) and are listed in the SNP database of the NCBI (National Center for Biotechnology Information). Peripheral leukocytes will be genotyped for PARP polymorphisms in the CPC with Dr. [name]'s laboratory. Particular attention will be given to the SNP, PARP1

Val762Ala, in which the variant allele contributes to dramatically lower PARP1 activity (Zhang et al. 2005). In addition, polymorphisms in XRCC1 will be assessed, as over-expression of XRCC1 decreases PARP1 activity. The SNP XRCC1 Arg399Glu resides in PARP1-interaction region (amino acid 314-402) in XRCC1 gene and Arg194Trp and Arg280Ile are correlated to altered risks to cancers and/or platinum sensitivity (Yuan et al., 2006; Skjelbred et al. 2006; Hao et al., 2004), though with inconsistent results (Zhai et al. 2006; Miao et al. 2006).

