1.3. Secondary Objectives

- 1.3.1. Phase 1 Portion:** Assess the toxicities of the combination of cediranib and olaparib in the treatment of recurrent ovarian, fallopian tube, or peritoneal cancer or metastatic triple-negative breast cancer. Assess clinical benefit, progression-free survival, and overall survival for patients treated with cediranib and olaparib.
- 1.3.2. Phase 2 Portion:** Assess tumor response, clinical response benefit (response or stable disease as defined by RECIST response criteria x 16 weeks), and overall survival (OS) for patients treated with cediranib and olaparib at the RP2D as compared with patients receiving olaparib alone.
- 1.3.3. Phase 2 Portion Translational Objectives:**
 - To evaluate the prognostic and predictive role of measured changes in functional vascular imaging using DCE-MRI between pre-study and day 3.

- To evaluate in an exploratory fashion the predictive or prognostic value of SNPs in key genes involved in angiogenesis and DNA repair.
- To evaluate the predictive value of baseline PBMC PAR incorporation on response to therapy.
- To measure early changes in vascular cytokine production and evaluate in an exploratory fashion that these changes may be predictive or prognostic, or differentially affected by the combination of agents.
- To evaluate early changes to circulating endothelial cells and if these changes are predictive or prognostic.
- To assess changes in measures of DNA damage and repair and angiogenesis in tumor cells (tissue and/or malignant effusions) and correlate to drug/drug/combination.

1.3.4. Phase 1-T (olaparib tablet) Portion: Assess the toxicities of the combination of cediranib and olaparib (tablet formulation) in the treatment of recurrent ovarian, fallopian tube, or peritoneal cancer. Assess clinical benefit, progression-free survival, and overall survival for patients treated with cediranib and olaparib (tablet formulation). Assess the pharmacokinetic profile of cediranib and olaparib (tablet formulation) when administered in combination.

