1. Cediranib tablet(s) in the morning on an empty stomach (at least 2 hours after eating)
2. Light meal ~1 hour after taking cediranib
3. Morning olaparib tablet(s) after light meal
4. Evening olaparib tablet(s) 12 hours after morning olaparib dose, taken after a light meal

Phase II

For the Phase 2 portion of this study, patients will be randomized in 1:1 ratio to one of the two following arms:

1. Olaparib 400mg BID (capsule)
2. Cediranib and olaparib at the RP2D (cediranib 30mg daily and olaparib 200mg BID (capsule)) derived from the Phase I portion of this study

Participants enrolled to the Phase II portion of the study will continue treatment with olaparib capsule formulation.

All patients must meet the eligibility criteria for the Phase II portion of the study, as outlined in Section 3. Patient randomization will be stratified based upon:

1. Prior receipt of anti-angiogenic therapy.
2. BRCA mutation status (carrier, non-carrier, unknown).

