5.1.4. Pre-Cycle 1 Therapy: Translational Component

- All patients will be *strongly* encouraged to participate in the translational component of the trial. Travel to and from the NCI and all costs of imaging, blood draws, biopsy, or fluid sampling done at the NCI will be provided in kind. A stipend to assist with cost of the local stay during this aspect of the trial will be provided, or the patient can elect hospital admission at no cost.
- Biopsiability will be determined prior to scheduling the NCI visit using most recent tumor imaging. This will be followed by an on-study chest/abdominal/pelvic CT with oral and IV contrast obtained the day of evaluation at NCI. A copy of this scan will be provided to the home institution for use in subsequent tumor measurements.
- Patients will be seen at NCI with a copy of their signed protocol consent from their home institution.
- Drug therapy will be initiated after acquisition of initial translational components and dispensed for the 28-day cycle.
- Translational component sample acquisition will occur:
 - Prior to starting therapy
 - Prior to day 3: 2-8 hours after the 5th dose of olaparib (d1 will start with the am dose) and the 3rd dose of cediranib (the first dose of cediranib will be administered at the same time as the first dose of olaparib).

Process	Pre-treatment	Day 3
Blood for PBMCs, DNA, and CECs	X	X
Plasma and serum for cytokines	X	X
DCE-MRI imaging	X	X
Biopsy: core of tumor, involved skin, or malignant effusion sampling	X	X

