8.2. Rationale for Selected Endpoints

These endpoints were selected to allow illustration of mechanism of the agents and potential interaction between the agents. They were also selected to investigate, in an exploratory fashion, whether any measures were predictive or prognostic, with the former being of greater interest.

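### The only comparison stated for the DCE-MRI parameters is before versus on therapy; a baseline-adjusted comparison of the randomised arms at day 3 should be added

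*Combined protocol and SAP*

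**What the plan says.** Section 8.4 (Functional Imaging) names two kinetic parameters, Ktrans and kep, "which will be used as continuous outcome variables in the analysis". It does not describe that analysis beyond one sentence: "Data obtained before and on therapy will be compared for changes as a result of decreases in angiogenesis". No arm, contrast or covariate is named.

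Two purposes are given for these data. Section 8.2 says of the translational endpoints in general: "These endpoints were selected to allow illustration of mechanism of the agents and potential interaction between the agents". It adds that they were also chosen to explore predictive or prognostic value, and that the predictive question is of greater interest. The formal objective in section 1.3.3 is "To evaluate the prognostic and predictive role of measured changes in functional vascular imaging using DCE-MRI between pre-study and day 3".

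On the design, section 5 says of Phase II that "patients will be randomized in 1:1 ratio to one of the two following arms": olaparib 400 mg BID alone, or cediranib 30 mg daily with olaparib 200 mg BID. Section 5.1.4 says "Drug therapy will be initiated after acquisition of initial translational components", and its table marks DCE-MRI at pre-treatment and at day 3 with no distinction by arm.

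Section 14 names between-arm analyses for PFS, response and clinical benefit, and overall survival. It gives none for imaging or any other translational endpoint.

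**The concern.** A change from the pre-treatment scan to day 3 is the sum of whatever the drugs did and whatever else altered the measurement between two scans. In the combination arm the drug part itself has two sources, because section 2.4.1 cites anti-angiogenic effects of PARP inhibition. A before/on comparison cannot divide that sum, yet the sentence in 8.4 assigns the change to reduced angiogenesis in advance.

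The trial already has what is needed to do better: a concurrent randomised arm on olaparib alone, and a baseline value for each scanned patient. Changes that are common to both arms cancel in a between-arm contrast and do not cancel in a before/on contrast.

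At stake is whether the imaging results can say anything reliable about mechanism and interaction. The primary comparison is not at stake: section 2.3.1 says the molecular imaging is for research purposes and is not used to assess RECIST response.

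**Working it through.** **No planned figure to reproduce.** The documents give no number scanned, SD, effect size, alpha or power for DCE-MRI. Every n, SD, fall and correlation below is an assumption. The only ceiling the documents offer is 41 evaluable patients per arm (section 14.2), and scanning is optional (section 9.2, footnote o), so the number may be much lower.

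**1. Before/on test when the drugs do nothing.** Let the log ratio of the day-3 to the pre-treatment value have mean log(1 − f), where f is a fall not caused by either drug, and standard deviation s. A two-sided paired t-test at 0.05 on n patients then follows a noncentral t distribution with n − 1 degrees of freedom and noncentrality √n × log(1 − f)/s. For n = 20 the critical value is 2.093.

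| Assumed fall f | Assumed SD s | Noncentrality (n = 20) | Rejection rate |
|---|---|---|---|
| 0 | any | 0 | 5% |
| 5% | 0.4 | √20 × (−0.0513)/0.4 = −0.57 | 8.5% |
| 10% | 0.3 | √20 × (−0.1054)/0.3 = −1.57 | 32% |
| 10% | 0.2 | √20 × (−0.1054)/0.2 = −2.36 | 61% |

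Holding f = 10% and s = 0.3 and changing only n gives 17% (n = 10), 25% (n = 15) and 46% (n = 30). More patients make the problem worse, because the test becomes better at detecting a change that is not due to treatment.

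**2. Between-arm test under the same conditions.** Simulation with no drug effect (20,000 trials per setting; 10, 20 or 41 per arm; pre/day-3 correlation r of 0.5, 0.7 or 0.9; a common fall of 0, 0.2 or 0.4 SD) compared the within-arm paired test with an analysis of covariance between arms.

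- The analysis of covariance rejected in 4.7% to 5.3% of trials in every setting.
- At n = 20 per arm and r = 0.7, the within-arm test declared a significant fall in 19% of trials with a 0.2 SD fall and 59% with a 0.4 SD fall. With no fall it did so in 2.6%, close to the nominal one-direction 2.5%.
- In the same two settings with a fall, exactly one arm was significant in 31% and 48% of trials. Setting two before/on tests side by side is therefore no substitute for a direct contrast.

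**3. What the between-arm analysis could detect.** For 80% power at two-sided 0.05, by normal approximation, the detectable day-3 difference in SD units is (1.96 + 0.84) × √(2/n × V). V is 1 − r² for analysis of covariance, 2(1 − r) for a between-arm change score, and 1 for the day-3 value alone. With n = 20 per arm:

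| r | Analysis of covariance | Change score | Day 3 only |
|---|---|---|---|
| 0.5 | 0.77 | 0.89 | 0.89 |
| 0.7 | 0.63 | 0.69 | 0.89 |
| 0.9 | 0.39 | 0.40 | 0.89 |

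The variance ratio of analysis of covariance to change score is (1 − r²)/(2(1 − r)) = (1 + r)/2. That is 0.75 at r = 0.5 and 0.90 at r = 0.8, a gain of 25% and 10%. This gain is over a between-arm change score. It is not a gain over the before/on comparison in 8.4, which answers a different question.

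**The case against.** **The plan does not choose the wrong analysis.** A reader might infer that 8.4 adopts the before/on comparison in place of an arm comparison. It does not: the sentence names no test and excludes nothing, in a section mainly about scheduling and acquisition. This objection stands. The point is an omission.

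**The formal objective is prognostic and predictive.** Objective 1.3.3 uses each patient's change, and an arm comparison of day-3 values does not test whether that change predicts outcome. This stands too, so the existing sentence should be supplemented and not replaced. The predictive question would need an arm-by-change model on outcome, which is also unspecified.

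**The arm contrast does not isolate cediranib.** It is tempting to say the randomised comparison shows what cediranib adds. Section 5 does not support that, because the olaparib dose differs between the arms. The contrast is regimen against regimen.

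**A fall in both arms may be real.** If olaparib reduces angiogenesis, a fall in the olaparib-alone arm is a true answer to the literal question in 8.4. Only non-drug change misleads on that question, and the documents give no evidence of its size. Random measurement error that is symmetric does not inflate a paired test. This limits the magnitude. It does not help the interaction aim, which needs the two regimens compared.

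**The scanned subset may not be a randomised comparison.** Participation is optional, the schema places recruitment before treatment but does not say before allocation, and no blinding of treatment is described. This stands and calls for reporting, as set out in the fix.

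**Cytokines are already framed comparatively.** Sections 1.3.3 and 2.3.2 raise differences with the combination. Neither states a method, so using the same model fills a gap.

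**Conclusion.** The point holds as an omission with a cost-free remedy. The single stated DCE-MRI comparison is uncontrolled and pre-assigns its cause, while scheduled data from both randomised arms would support a controlled, baseline-adjusted one. For the mechanism and interaction aim of 8.2 the controlled comparison is clearly better.

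Its size cannot be fixed from the documents. Over the assumptions shown for 20 patients, the before/on rejection rate without any drug effect runs from the nominal 5% to 61%. A reader should not take any one of these as the trial's actual false-positive rate. The between-arm rate stays near 5%, provided non-drug change is the same in both arms and the scanned patients remain comparable by allocation. The importance is low because the endpoint is exploratory.

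**What to change.** Keep the within-patient change for the prognostic and predictive objective in 1.3.3, and add to section 8.4:

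> Day-3 log Ktrans and log kep will be compared between randomised arms by analysis of covariance with the log pre-treatment value as covariate, reporting the arm difference and 95% interval; within-arm changes are descriptive and are not by themselves taken as evidence of a treatment effect.

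Use the same model for the day-3 cytokine and circulating endothelial cell values. State that the contrast is the combination regimen against the olaparib-alone regimen. Report the number scanned in each arm and whether patients opted in before allocation was known.

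The cost is a few sentences of text. No additional patients, scans, samples or readers are needed.

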8.9. IHC/IF

Tumor samples (core biopsy recuts and/or effusion cell pellets) will be used for IHC or immunofluorescence (IF) to examine both vascular and DNA repair endpoints using validated SOPs. Scoring will be based upon number of positive cells and/or number of foci as pertinent to the endpoint. The following endpoints will be examined, with the following prioritization:

- RAD51 (foci per cell)
- γ H2AX (foci per cell)
- VEGF
- CD31 or other measure of microvessels
- Pending tissue, some or all of the following may be examined: PARP1, BRCA1, ERCC1, XRCC1, other related endpoints.

8.10. Proteomic Endpoints

Core biopsy or effusion cell pellets will be examined in a blinded fashion in the fee-for-service MD Anderson Reverse Phase Protein Array Core. This provides a comprehensive analysis of total and phosphorylated proteins involved in invasion, cell cycle, proliferation, DNA repair. Data will be analyzed for change over time trends, as well as patterns of protein expression. These endpoints coupled with the IHC/IF results are aimed to evaluate HR competence (RAD51+) and changes in vascular signaling.

8.11. BRCA Mutation Status

No testing of BRCA mutation status is currently planned; however, research assessment of homologous recombination competence and endpoints in DNA damage repair pathways may be performed on available samples pending funding either within the NCI or with a collaborative partner outside of the NCI.

8.12. Family Risk Assessment

All patients will be asked to fill out the family risk assessment form (Appendix I). Where mutation is unknown, BRCAPro score will be calculated. This will be examined as a variable against outcome and HRD status in the translational endpoints.

8.13. Post-progression Tissue Analysis

At the time of progression, where possible, core needle biopsies from a new lesion or site of progression will be obtained. The biopsy will be taken at the time of drug discontinuation or within the 30d follow up period pending patient consent. This research biopsy will be optional and performed only if there is minimal risk. In BRCA mutation carriers, research sequencing of BRCA will be performed from the tissue to test for the presence of secondary mutations that can restore BRCA function, as well as the presence of other proteins (e.g. 53BP1), identified as potentially mediating PARP-inhibitor resistance. Pending tissue availability, other markers of DNA repair and vascular endpoints such (e.g. RAD51, γ H2AX, VEGFR, CD31) will also be examined.

